6.11.1. Primary Outcome and Methodology

The validated IGA for AD uses the clinical characteristics of erythema, papulation/induration, oozing/crusting, and lichenification to produce a single-item score ranging from 0 to 4. The primary analysis of the study is to estimate the effect of long-term therapy with baricitinib on responders and partial responders at the entry of Study JAHN by evaluating the proportion of patients with a response of IGA 0 or 1 assessed at Weeks 16, 36, and 52 using the mITT population, assuming that treatment response disappears after the patient is rescued or discontinued study or study treatment. This will serve as the primary estimand. In this estimand, missing data due to the application of the censoring rule and the occurrence of other noncensor intercurrent events will be imputed using the NRI method described in Section 6.4.1. A logistic regression analysis as described in Section 6.2.3 will be used for the comparisons. The odds ratio, the corresponding 95% CIs and p-value, as well as the treatment differences and the corresponding 95% CIs, will be reported.

For analyses on and after the February 2021 DBL, mLOCF will be used as Primary approach for all categorical endpoints (including PROs) and NRI will be used as supportive sensitivity.

6.11.2. Secondary and Exploratory Efficacy Analyses

There will be no adjustment for multiple comparisons for any analyses. The secondary and exploratory efficacy analyses are detailed in Table JAHN.6.4. Health outcomes analyses are described in Section 6.12.

For patients entering the downtitration and withdrawal substudy who need to be retreated, a summary of treatment responses containing proportion of patients with IGA (0, 1, 2), IGA (0, 1), and EASI75 response will be provided. A summary of the time to retreatment will also be provided.

Note that the exploratory efficacy analyses on a continuous outcome that is measured over time use a slightly different estimand which is to estimate the effect of long-term therapy with baricitinib on a specific endpoint evaluated at specified time points using the mITT population assuming all patients remained in their treatment throughout the defined period of the study.

6.11.3. Sensitivity Analyses

Sensitivity analyses are included to demonstrate robustness of analyses methods using different censoring rules, populations, and analyses assumptions. Sensitivity analyses for select outcomes have been previously described and include the following:

- analysis of select continuous outcomes with ANCOVA (Section 6.2.3), with missing data imputed using mLOCF (Section 6.4.3)
- analysis of select continuous outcomes in the randomized withdrawal and downtitration substudy using Week 52 as the baseline
- analysis of selected outcomes (IGA, EASI, ITCH-NRS), with missing data imputed using mLOCF

For analyses on and after the February 2021 DBL, NRI will be used as supportive sensitivity.

6.12. Health Outcomes/Quality-of-Life Analyses

The general methods used to summarize health outcomes and quality-of-life measures, including the definition of baseline value for assessments, are described in Section 6.2.

Health outcomes and quality-of-life measures will generally be analyzed according to the formats discussed in Section 6.2.

Table JAHN.6.6 includes the descriptions and derivations of the health outcomes and quality-of-life measures.

Table JAHN.6.7 provides the detailed analyses including analysis type, method and imputation, population, time point, and comparisons for health outcomes and quality-of-life measures.

Table JAHN.6.6. Description and Derivation of Health Outcomes and Quality-of-Life Measures

Measure	Description	Variable	Derivation / Comment	Imputation Approach if Missing Components
Itch Numeric Rating Scale (NRS)	The Itch Numeric Rating Scale (NRS) is a patient-administered, 11-point horizontal scale anchored at 0 and 10, with 0 representing “no itch” and 10 representing “worst itch imaginable.” Overall severity of a patient’s itching is indicated by selecting the number that best describes the worst level of itching in the past 24 hours (Naegeli et al. 2015; Kimball et al. 2016). Refer to Section 6.2.2 for details on how to calculate the weekly score which will be used in the continuous analysis.	
 ▪ Itch NRS score 	Single item. Range 0-10. Refer to Section 6.2.2 on how to derive the weekly score.	Refer to Section 6.2.2 on how to derive the weekly score.
		
 ▪ Change from baseline in Itch NRS ▪ Percent change from baseline in Itch NRS 	Change from baseline: observed Itch score – baseline Itch score % change from baseline: $100 \times \frac{\text{Observed score} - \text{Baseline}}{\text{Baseline}}$	Missing if baseline or observed value is missing.
		
 ▪ 4-point Itch improvement in subgroup of patients with baseline Itch NRS ≥ 4 	Change from baseline ≤ -4 and baseline ≥ 4	Missing if baseline is missing or <4 or observed value is missing.
Skin Pain Numeric Rating Scale (NRS)	Skin Pain NRS is a patient-administered, 11-point horizontal scale anchored at 0 and 10, with 0 representing “no pain” and 10 representing “worst pain imaginable.” Overall severity of a patient’s skin pain is indicated by selecting the number that best describes the worst level of skin pain in the past 24 hours. Refer to Section 6.2.2 for details on how to calculate the weekly score which will be used in the continuous analysis.	
 ▪ Skin Pain NRS score 	Single item; range 0-10. Refer to Section 6.2.2 on how to derive the weekly score.	Refer to Section 6.2.2 on how to derive the weekly score.
		
 ▪ Change from baseline in Skin Pain NRS 	Change from baseline: observed skin pain score – baseline skin pain score	Missing if baseline or observed value is missing.

Measure	Description	Variable	Derivation / Comment	Imputation Approach if Missing Components
Atopic Dermatitis Sleep Scale (ADSS)	The Atopic Dermatitis Sleep Scale (ADSS) is a 3-item, patient-administered questionnaire developed to assess the impact of itch on sleep including difficulty falling asleep, frequency of waking, and difficulty getting back to sleep last night. Patients rate their difficulty falling asleep and difficulty getting back to sleep, items 1 and 3, respectively, using a 5-point Likert-type scale with response options ranging from 0 “not at all” to 4 “very difficult.” Patients report their frequency of waking last night, item 2, by selecting the number of times they woke up each night, ranging from 0-29 times. The ADSS is designed to be completed each day with respondents thinking about sleep “last night.” Each item is scored individually. Refer to Section 6.2.2 for details on how to calculate the weekly score which will be used in the continuous analysis.	
 ▪ Item 1 score of ADSS ▪ Item 2 score of ADSS ▪ Item 3 score of ADSS 	Single items: Item 1, range 0-4; Item 2, range 0-29; Item 3, range 0-4. Refer to Section 6.2.2 on how to derive the weekly score.	Refer to Section 6.2.2 on how to derive the weekly score.
		
 ▪ Change from baseline in score of Item 1 of ADSS ▪ Change from baseline in score of Item 2 of ADSS ▪ Change from baseline in score of Item 3 of ADSS 	Change from baseline: observed ADSS item score – baseline ADSS item score	Missing if baseline or observed value is missing.
Patient Global Impression of Severity– Atopic Dermatitis (PGI-S-AD)	The PGI-S-AD is a single-item question asking the patient how they would rate their overall AD symptoms over the past 24 hours. The 5 categories of responses range from “no symptoms” to “severe.” Refer to Section 6.2.2 for details on how to calculate the weekly score which will be used in the continuous analysis.	PGI-S-AD score	Single item. Range 1-5. Refer to Section 6.2.2 on how to derive the weekly score.	Refer to Section 6.2.2 on how to derive the weekly score.
		Change from baseline in PGI-S-AD	Change from baseline: observed PGI-S-AD score – baseline PGI-S-AD score	Missing if baseline or observed value is missing.

Measure	Description	Variable	Derivation / Comment	Imputation Approach if Missing Components
Patient-Oriented Eczema Measure (POEM)	The POEM is a simple, 7-item, patient-administered scale that assesses disease severity in children and adults. Patients respond to questions about the frequency of 7 symptoms (itching, sleep disturbance, bleeding, weeping/oozing, cracking, flaking, and dryness/roughness) over the last week. Response categories include “No days,” “1-2 days,” “3-4 days,” “5-6 days,” and “Every day” with corresponding scores of 0, 1, 2, 3, and 4, respectively. Scores range from 0-28 with higher total scores indicating greater disease severity (Charman et al. 2004).	POEM score	POEM total score: sum of questions 1-7, range 0-28.	If a single question is left unanswered, then that question is scored as 0. If more than 1 question is unanswered, then the tool is not scored. If more than 1 response is selected, then the response with the highest score is used.
		Change from baseline in POEM score	Change from baseline: observed POEM score – baseline POEM score	Missing if baseline or observed value is missing.
Hospital Anxiety Depression Scale (HADS)	The HADS is a 14-item self-assessment scale that determines the levels of anxiety and depression that a patient is experiencing over the past week. The HADS utilizes a 4-point Likert scale (eg, 0-3) for each question and is intended for ages 12-65 years (Zigmond and Snaith 1983; White et al. 1999). Scores for each domain (anxiety and depression) can range from 0-21, with higher scores indicating greater anxiety or depression (Zigmond and Snaith 1983; Snaith 2003).	HADS score for anxiety and depression domains	Anxiety domain score is sum of the 7 anxiety questions, range 0-21; Depression domain score is sum of the 7 depression questions, range 0-21.	N/A – partial assessments cannot be saved.
		
 Change from baseline in HADS domain 	Change from baseline: observed HADS domain score – baseline HADS domain score	Missing if baseline or observed value is missing.

Measure	Description	Variable	Derivation / Comment	Imputation Approach if Missing Components
Dermatology Life Quality Index (DLQI)	The Dermatology Life Quality Index (DLQI) is a simple, patient-administered, 10-item, validated, quality-of-life questionnaire that covers 6 domains including symptoms and feelings, daily activities, leisure, work and school, personal relationships, and treatment. The recall period of this scale is over the “last week.” Response categories include “a little,” “a lot,” and “very much,” with corresponding scores of 1, 2, and 3, respectively, and “not at all,” or unanswered (“not relevant”) responses scored as 0. Scores range from 0-30 with higher scores indicating greater impairment of quality of life. A DLQI total score of 0-1 is considered as having no effect on a patient’s health-related QoL (Hongbo et al. 2005), and a 4-point change from baseline is considered as the minimal clinically important difference threshold (Khilji et al. 2002; Basra et al. 2015).	
 ▪ Symptoms and feelings domain 	Sum of Questions 1 and 2, range 0 to 6.	N/A – partial assessments cannot be saved.
		
 • Daily activities domain 	Sum of Questions 3 and 4, range 0 to 6.	N/A – partial assessments cannot be saved.
		
 • Leisure domain 	Sum of Questions 5 and 6, range 0 to 6.	N/A – partial assessments cannot be saved.
		
 • Work and school domain 	Sum of Questions 7 and 7B (if it is answered), range 0 to 3. Responses of “yes” and “no” on Question 7 are given scores of 3 and 0 respectively. If Question 7 is answered “no” then Question 7b is answered with “a lot”, “a little”, “not at all” getting scores of 2, 1, and 0 respectively.	N/A – partial assessments cannot be saved.
		
 • Personal relationships domain 	Sum of Questions 8 and 9, range 0-6.	N/A – partial assessments cannot be saved.
		
 • Treatment domain 	Question 10, range 0-3.	N/A – partial assessments cannot be saved.
		
 • DLQI total score 	DLQI total score: sum of all 6 DLQI domain scores, range 0-30.	N/A – partial assessments cannot be saved.
		
 • Change from baseline in DLQI 	Change from baseline: observed DLQI score – baseline DLQI score	Missing if baseline or observed value is missing.

Measure	Description	Variable	Derivation / Comment	Imputation Approach if Missing Components
Work Productivity and Activity Impairment: Atopic Dermatitis (WPAI-AD)	The Work Productivity and Activity Impairment Questionnaire–Atopic Dermatitis (WPAI-AD) records impairment due to AD during the past 7 days. The WPAI-AD consists of 6 items grouped into 4 domains: absenteeism (work time missed), presenteeism (impairment at work/reduced on-the-job effectiveness), work productivity loss (overall work impairment/absenteeism plus presenteeism), and activity impairment. Scores are calculated as impairment percentages (Reilly et al. 1993), with higher scores indicating greater impairment and less productivity.	
 ▪ Employment status 	Question (Q)1	Single item, missing if missing.
		
 • Change in employment status 	Employed at baseline and remained employed: Q1 = 1 at postbaseline visit and at baseline visit. Not employed at baseline and remain unemployed: Q1 = 0 at postbaseline visit and at baseline visit.	Missing if baseline or observed value is missing.
		
 • Percentage of absenteeism 	Percent work time missed due to problem: $(Q2 / [Q2 + Q4]) * 100$	If Q2 or Q4 is missing, then missing.
		
 • Change from baseline in absenteeism 	Change from baseline: observed absenteeism – baseline absenteeism	Missing if baseline or observed value is missing.
		
 • Percentage of presenteeism 	Percent impairment (reduced productivity while at work) while working due to problem: $(Q5 / 10) * 100$	If Q5 is missing, then missing.
		
 • Change from baseline in presenteeism 	Change from baseline: observed presenteeism – baseline absenteeism	Missing if baseline or observed value is missing.
		
 • Overall work impairment 	Percent overall work impairment (combines absenteeism and presenteeism) due to problem: $(Q2 / [Q2 + Q4] + [(1 - Q2 / (Q2 + Q4)) * (Q5 / 10)]) * 100$	If Q2, Q4, or Q5 is missing, then missing.
		
 • Change from baseline in work impairment 	Change from baseline: observed work impairment – baseline work impairment	Missing if baseline or observed value is missing.
		
 • Percentage of impairment in activities 	Percent activity impairment (performed outside of work) due to problem: $(Q6 / 10) * 100$	If Q6 is missing, then missing.

 • Change from baseline in impairment in activities 	Change from baseline: observed impairment in activities – baseline impairment in activities	Missing if baseline or observed value is missing.		

Measure	Description	Variable	Derivation / Comment	Imputation Approach if Missing Components

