		Period 2 non-substudy population Open-label Period 2 non-substudy population	Descriptive using mLOCF and NRI	Week 52 to 200	Exploratory Primary for mLOCF Sensitivity for NRI
		Long term Baricitinib 4 mg population	Descriptive using observed, NRI and mLOCF	Weeks 52-200	Exploratory
Work Productivity and Activity Impairment: Atopic Dermatitis (WPAI-AD)	Observed and change from baseline in employment status: 
 ▪ absenteeism ▪ presenteeism ▪ overall work impairment impairment in activities	mITT population from originating combination therapy study - responders, partial responders	Descriptive using observed and mLOCF	Weeks 0-52	Exploratory analysis
		mITT population from originating combination therapy study - nonresponders	MMRM using observed Descriptive using mLOCF	Weeks 0-52	Exploratory analysis

Measure	Variable	Population ^a (Section 6.2.1)	Analysis Method ^b (Section 6.2.3)	Time Point	Analysis Type
		mITT population from open-label study	Descriptive using observed and mLOCF	Weeks 0-52	Exploratory analysis
European Quality of Life-5 Dimensions-5 Levels (EQ-5D-5L)	Observed and change from baseline in: 
 ▪ EQ-5D mobility ▪ EQ-5D self-care ▪ EQ-5D usual activities ▪ EQ-5D pain/discomfort EQ-5D anxiety/depression	mITT population from originating combination therapy study - responders, partial responders	Descriptive using observed and mLOCF	Weeks 0-52	Exploratory analysis
		mITT population from originating combination therapy study - nonresponders	MMRM using observed Descriptive using mLOCF	Weeks 0-52	Exploratory analysis
		mITT population from open-label study	Descriptive using observed and mLOCF	Weeks 0-52	Exploratory analysis

Abbreviations: ANCOVA = analysis of covariance; EE = efficacy evaluable; IGA = Investigator’s Global Assessment; mITT = modified intent-to-treat; mLOCF = modified last observation carried forward; MMRM = mixed-model repeated measures; NRI = nonresponder imputation; VAS = visual analog scale.

- ^a Populations from originating studies for reporting periods of Week 0-52 are on the mITT population; they are reported by responder status from originating study: responders, partial responders, responders + partial responders, and nonresponders.
- ^b All categorical endpoints use NRI, unless otherwise stated.
- ^c Descriptive using observed data for the endpoints beyond Week 104, unless otherwise stated.

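### WPAI-AD overall work impairment is set to missing when Q5 is blank, even where the SAP's own formula fixes it at 100%, and change in employment status has no level for a change

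*SAP*

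**What the plan says.** SAP Section 6.12, Table JAHN.6.6, derives the WPAI-AD scores. Three of them matter here.

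- **Absenteeism** is 100 × Q2/(Q2 + Q4). Its missing-component rule is "If Q2 or Q4 is missing, then missing", so Q5 plays no part.
- **Presenteeism** is 100 × Q5/10, described as "Percent impairment (reduced productivity while at work) while working due to problem".
- **Overall work impairment** is described as "Percent overall work impairment (combines absenteeism and presenteeism) due to problem". It adds to absenteeism the Q5 impairment weighted by the share of time worked. Its rule is "If Q2, Q4, or Q5 is missing, then missing", with no exception.

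Higher scores mean greater impairment.

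Table JAHN.6.7 analyses these scores for Weeks 0-52. Responders, partial responders and open-label patients get descriptive summaries of observed and mLOCF data. Nonresponders get MMRM on observed data plus a descriptive mLOCF summary. Table APP.1.4, for the addendum, uses observed data only, for Weeks 0-24. Every one of these analyses is labelled exploratory.

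For change in employment status, Table JAHN.6.6 gives two levels. The first is "Employed at baseline and remained employed: Q1 = 1 at postbaseline visit and at baseline visit"; the second is the matching level for patients unemployed at both visits.

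**The concern.** Q5 rates impairment during work. A patient who did no work in the recall week has nothing to rate and may well leave it blank. If so, the rule removes the overall score exactly when the patient has lost the whole working week to AD. The other two answers already determine that score, and it is the top of the scale.

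Missingness would then follow from the outcome value itself. Section 6.4.2 bases the MMRM on missing at random, and the model terms in Section 6.2.3 do not include absenteeism, the variable that would reveal the lost score. Section 6.4.3 has mLOCF carry forward the last nonmissing postbaseline value, which would usually come from a visit when the patient was still working.

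The employment variable is a separate gap in the same block. It is named for change, but its two levels cover only patients who did not change.

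**Working it through.** **Inputs.** The formulas and missing rules come from Table JAHN.6.6, mLOCF from Section 6.4.3 and the analyses from Table JAHN.6.7. I read Q2 as time missed because of AD and Q4 as time worked, from the absenteeism formula. The SAP states no figure for this point, so there is none to reproduce.

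**Step 1: the score when no work was done.** Let A = Q2/(Q2 + Q4). Overall impairment = 100 × [A + (1 − A) × Q5/10]. With Q2 > 0 and Q4 = 0, A = 1 and the weight on Q5 is 1 − A = 0, so the score is 100. Evaluating the formula for Q2 = 1 to 80 and Q5 = 0 to 10 gave 100 every time.

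**Step 2: the same record under the two missing rules.** Take Q2 = 40, Q4 = 0, Q5 blank.
- Absenteeism = 100 × 40/40 = 100%.
- Overall impairment = missing.

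Overall impairment minus absenteeism is 100 × (1 − A) × Q5/10, which is never negative. Overall impairment therefore cannot be below absenteeism, and here it could only be 100.

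**Step 3: what each analysis does with the record.**
- Observed summaries drop it.
- The MMRM omits it and relies on missing at random.
- mLOCF carries an earlier postbaseline score if there is one. Example with assumed answers: an earlier visit with Q2 = 8, Q4 = 32, Q5 = 5 scores 100 × [0.2 + 0.8 × 0.5] = 60%, so 60 is entered instead of 100.

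A carried score can equal 100 from a working week only if Q5 was 10. With Q4 of at least 1, whole hours up to 40 and Q5 of 9 or less, the maximum is 100 × [40/41 + (1/41) × 0.9] = 99.76.

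**Step 4: illustrative size.** The documents give no rates. Assume a share f of employed patients at a visit have Q2 > 0, Q4 = 0 and a blank Q5, and the others average 20%. The mean with the score retained is 100f + 20(1 − f), and the observed-case mean is 20. The last column assumes that every affected patient carries forward 60, so that the shortfall is f × (100 − 60).

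| f | Mean with score retained | Observed mean | Shortfall, observed | Shortfall, mLOCF |
|---|---|---|---|---|
| 1% | 20.8 | 20.0 | 0.8 | 0.4 |
| 3% | 22.4 | 20.0 | 2.4 | 1.2 |
| 5% | 24.0 | 20.0 | 4.0 | 2.0 |

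Over a wider grid, f = 2% to 10% and others averaging 20% to 40%, the observed shortfall is f × (100 − mean). It runs from 0.02 × 60 = 1.2 to 0.10 × 80 = 8.0 points.

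**Step 5: change from baseline.** Table JAHN.6.6 makes change missing if either value is missing. If the lost score is postbaseline, a poor result is removed. If it is the baseline score, the patient leaves the change analysis altogether; one who went from 100 to 20 would have contributed 20 − 100 = −80, a large improvement. The direction of bias in change scores is therefore not fixed.

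**Step 6: employment levels.** Q1 is 1 or 0 at each of two visits, giving four combinations: 1→1, 0→0, 1→0 and 0→1. Table JAHN.6.6 defines the first two only. Its missing rule applies only when the baseline or observed value is missing, so patients who changed are not excluded; they simply have no category.

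**The case against.** The strongest objection is that the mechanism is not in the documents. Neither shows the questionnaire, its skip pattern or the device settings. If Q5 is always answered, nothing is lost. That stands: the blank is an inference from the wording of the presenteeism score. There is some indirect support, because Table JAHN.6.6 says partial HADS and DLQI assessments cannot be saved, whereas for the WPAI it writes item-level missing rules. That suggests blanks were thought possible, but it does not prove it.

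Several stronger readings are tempting, and the documents do not support them.

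- **That the lost scores are always replaced by milder ones.** Only mLOCF substitutes a value, and only if there is a baseline and an earlier postbaseline score.
- **That impairment is biased low everywhere.** This holds for observed levels. Change scores can go either way (Step 5).
- **That a dose difference would vanish.** Absenteeism keeps these patients at 100% and gets the same analyses. Only the composite score loses them.
- **That job loss is not counted anywhere.** Employment status by visit is still summarised, so net shifts can be seen. What is undefined is the individual transition.
- **That a yes/no item will be fitted by MMRM.** The row headed "Observed and change from baseline in employment status" in Table JAHN.6.7 runs straight into the percentage scores, which may be a layout effect. Sections 6.2.3 and 6.4.2 reserve MMRM for continuous variables, and Table APP.1.4 lists employment status separately.

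It is also fair to say that the sizes rest entirely on assumed rates, and that the Revision History (Section 3, Version 8) records data to Week 104 as already locked.

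**Conclusion.** The scoring rule is wrong as written. When Q2 > 0 and Q4 = 0, overall work impairment is 100% by the SAP's own formula, yet the rule makes it missing if Q5 is blank. I found nothing elsewhere in the SAP or protocol that restores the score.

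Whether this affects results depends on Q5 actually being left blank by patients who did no work. The 0.8 to 4.0 point understatement of observed means is an illustration under the assumptions in Step 4, not an estimate. The missing employment transitions are a definite but minor gap that does not depend on Q5.

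No primary or secondary conclusion is touched. This is a small correction to an exploratory outcome.

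**What to change.** In Table JAHN.6.6:

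- If Q2 > 0 and Q4 = 0, set overall work impairment to 100 regardless of Q5. In all other cases keep it missing when any of the three items is missing.
- Leave presenteeism missing when Q4 = 0 and Q5 is blank, since there was no work to rate.
- State that Q2 = Q4 = 0 is treated as missing, because the ratio is 0/0.
- Add two employment levels: employed at baseline and not employed at the visit; not employed at baseline and employed at the visit.

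In Table JAHN.6.7, give employment status its own descriptive row, as in Table APP.1.4.

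Before re-deriving anything, count the records with Q2 > 0, Q4 = 0 and Q5 blank. If there are none, the scoring change is only a clarification.

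The cost is a few lines of SAP text and the re-derivation of one exploratory score and one categorical variable from data already collected. Because the data are locked, this would be reported as an update or a note to the existing results.
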